4.1.2.1. Continuous Abstinence

The comparisons for the 2 continuous abstinence efficacy objectives will be between experimental arms and the placebo arm, as follows:

- Continuous abstinence from Week 6 to Week 24: Arm B (cytisinicline 6 weeks) vs Arm A (placebo)
- Continuous abstinence from Week 12 to Week 24: Arm C (cytisinicline 12 weeks) vs Arm A (placebo).

For the comparison of Arm A to Arm B (secondary objective 1), success for the continuous abstinence from Week 6 to Week 24 endpoint will be defined as having all of the following observed:

- Abstinence determined at the primary evaluation (Weeks 3-6), and
- At the Week 7 to Week 11 visits, subject self-report of abstinence since the last clinic visit together with biochemical verification of abstinence, and
- At the Week 12 visit, subject self-report of abstinence since the last clinic visit together with biochemical verification of abstinence, and
- Self-reported abstinence during the Week 16 to Week 24 Follow-up period, defined as smoking up to a total of 5 cigarettes at the attended Week 16, Week 20, and Week 24 visits together with biochemical verification of abstinence at each attended visit. (Only one visit, either Week 16 or Week 20, is allowed to be missing.)

For the comparison of Arm A to Arm C (secondary objective 2), success for the continuous abstinence from Week 12 to Week 24 endpoint will be defined as having all of the following observed:

- Abstinence determined at the primary evaluation (Weeks 9-12), and
- Self-reported abstinence during the Week 16 to Week 24 Follow-up period, defined as smoking up to a total of 5 cigarettes at the attended Week 16, Week 20, and Week 24 visits together with biochemical verification of abstinence at each attended visit. (Only one visit, either Week 16 or Week 20, is allowed to be missing.)

Any other outcome will be regarded as a failure. There are therefore two types of failure for the subject: (1) subjects with adequate data that they are not abstinent at any time (either by the subject's self-report or CO ≥ 10 ppm) and (2) subjects having insufficient data to be determined as a success for continuous abstinence.

Statistical methods for the continuous abstinence endpoints are described in Section 10.1.3.

4.1.2.2. Reduction in Risk of Relapse (Relapse-Free)

For the comparison of Arm C to Arm B (secondary objective 3), relapse free (success of not having relapsed) from Weeks 3-6 through to Week 24 will be defined as having the following observed after initial abstinence (ie, primary success criteria) is determined from Weeks 3-6:

- At the Week 12 visit, subject self-report of abstinence (relapse-free) since the last clinic visit together with biochemical verification of abstinence, and
- Self-reported abstinence (relapse-free) during the Week 16 to Week 24 Follow-up period, defined as smoking up to a total of 5 cigarettes at the attended Week 16, Week 20, and Week 24 visits together with biochemical verification of abstinence at each attended visit. (Only one visit, either Week 16 or Week 20, is allowed to be missing.)

Subjects not observed to meet the above success criteria will be regarded as having relapsed to the secondary efficacy 3 outcome. Non-success or relapse will have two types: (1) subjects with adequate data that fail to meet the above criteria, and (2) subjects having insufficient data to be assessed as a success. Note: subjects not abstinent at Week 6 (eg, Weeks 3-6) will be regarded as having already relapsed.

Statistical methods for the reduction in risk of relapse (relapse free) endpoint are described in Section 10.1.3.

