
Studies have been conducted by Achieve Life Sciences evaluating cytisinicline at 1.5 mg and 3 mg dose levels in the downward 25-day titration schedule as well as in a simplified three times daily (TID) schedule. The 3 mg TID schedule for cytisinicline in the ACH-CYT-09 Phase 2b (ORCA-1) trial showed the highest level of prolonged abstinence starting from the End-of-Treatment (Week 4) through Week 8 (abstinence rate of 30% compared to 8% for placebo [$p=0.005$]). The 3 mg TID schedule also showed a well-tolerated safety profile and treatment compliance was high at 97.6%. Since the 3 mg TID schedule is a more simplified schedule and showed significantly higher abstinence at 30%, longer treatment could possibly increase the abstinence rate. The Phase 3 program for cytisinicline includes two separate Phase 3 trials that are evaluating 3 mg cytisinicline TID as a slightly longer treatment duration of 42 days/6 weeks (instead of 25 days) as well as repeating that duration for a total of 84 days/12 weeks treatment (similar to the duration of varenicline treatment). The first Phase 3 (ORCA-2) trial has completed enrollment but is ongoing in study evaluations. This second Phase 3 (ORCA-3) study mirrors the ORCA-2 trial in study design, safety/efficacy evaluations, and statistical criteria, while being conducted in parallel at different clinical sites.

All subjects are to receive standard behavioral support for smoking cessation during the study. Subjects are to be randomized to one of three arms A, B, or C, where the intended interventions are placebo for 12 weeks plus behavioral support (Arm A), 3 mg cytisinicline TID for 6 weeks followed by placebo for 6 weeks plus behavioral support (Arm B), and 3 mg cytisinicline TID for 12 weeks plus behavioral support (Arm C).

The primary outcome measure is abstinence during the last 4 weeks of cytisinicline treatment compared to the placebo arm (Weeks 3-6 for comparison of Arm B vs Arm A; Weeks 9-12 for comparison of Arm C vs Arm A). The secondary outcome measure is abstinence continuing to Week 24 post randomization in the cytisinicline arms compared to the placebo arm (Weeks 6-24 for comparison of Arm B vs Arm A; Weeks 12-24 for comparison of Arm C vs Arm A). If the primary outcome of abstinence is significant for both 6 and 12 weeks of cytisinicline treatment, reduction in risk of relapse for those subjects achieving abstinence within a Week 3-6 period will be compared in Arm C vs Arm B from Week 7 to Week 24.

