CO-verified 7-day point abstinence rates at EOT (Week 4) were statistically higher in all cytisinicline treatment arms compared to placebo: 45% and 42% for the 1.5 mg and 3 mg downward titration arms and 48% and 50% for the 1.5 mg and 3 mg TID arms, respectively, compared to 10% for the placebo arms (Figure 1).

Continuous abstinence as of the Week 5 assessment through to the Week 8 assessment (total of 4 weeks of continual abstinence after the end of treatment) is also shown in Figure 1. The TID schedule for cytisinicline had statistically higher continuous abstinence rates compared to placebo, with subjects in the 3 mg cytisinicline TID arm having the highest continuous abstinence rate at 30% compared to 8% for placebo. Subjects in the 3 mg TID arm also had higher odds for continuous abstinence from cigarettes from Week 5 to Week 8 compared with placebo (OR: 5.04, 95% CI: 1.42, 22.32). The OR for the 1.5 mg TID arm was 4.33 (95% CI:

1.21, 19.30). On the downward titration schedule, the ORs for the 1.5 mg and 3 mg arms were 3.23 (95% CI: 0.86, 14.85) and 2.24 (95% CI: 0.55, 10.82), respectively.

No subject experienced a serious adverse event. No new or unexpected adverse events were identified during the study. Most adverse events were mild or moderate in intensity; only 2 (0.8%) were severe in intensity, and both were unrelated to study drug. About half of the adverse events (52.9%) were not related or unlikely to be related to the study drug. Most (95.3%) adverse events did not result in a change in dosing, and the subject was considered recovered (88.2%) during the study. A total of 3 subjects who received cytisinicline and 2 subjects who received placebo discontinued study treatment early due to an adverse event. Adverse events experienced by $\geq 2\%$ of subjects in the trial are summarized in [Table 3](#).

Table 3: ORCA-1 Study: Most Common Treatment-emergent Adverse Events Experienced by $\geq 2\%$ of Subjects

	Cytisinicline Downward Titration Schedule		Cytisinicline TID Schedule		Pooled Placebo (N=51) n (%)	All Subjects (N=254) n (%)
	1.5 mg (N=51) n (%)	3 mg (N=50) n (%)	1.5 mg (N=52) n (%)	3 mg (N=50) n (%)		
Upper respiratory tract infection	3 (5.9)	2 (4.0)	5 (9.6)	3 (6.0)	7 (13.7)	20 (7.9)
Abnormal dreams	4 (7.8)	7 (14.0)	4 (7.7)	3 (6.0)	1 (2.0)	19 (7.5)
Nausea	5 (9.8)	3 (6.0)	1 (1.9)	3 (6.0)	5 (9.8)	17 (6.7)
Insomnia	3 (5.9)	4 (8.0)	4 (7.7)	3 (6.0)	1 (2.0)	15 (5.9)
Headache	1 (2.0)	1 (2.0)	6 (11.5)	2 (4.0)	2 (3.9)	12 (4.7)

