7.3.2. Primary Endpoint

Smoking abstinence during the last 4 weeks of treatment as the primary endpoint mirrors the prior varenicline Phase 3 trials and other smoking cessation trials for regulatory approval. Most of these prior Phase 3 trials had a “grace” period with success determined as having 4 weeks abstinence during the last 4 weeks of treatment. For varenicline, treatment was for 12 weeks with the first 8 weeks as a “grace” period and weekly assessments at Weeks 9-12 while on treatment was the primary endpoint assessment. Arm B in this study will assess the benefit of a shorter, 6-Week cytisinicline treatment having the first 2 weeks as a “grace period” and weekly assessments at Weeks 3-6 while on treatment as the primary endpoint assessment. Arm C in this study will mirror that same treatment duration as varenicline with weekly assessments at Weeks 9-12 while on treatment as the primary endpoint assessment.

Cytisinicline treatment was developed as a shorter treatment for smoking cessation, especially for smokers who do not want to commit to 12 weeks of treatment. However, the commercial 25-day treatment period may be too short on treatment, since smoking relapse appeared high in ORCA-1 from the end of treatment abstinence (Week 4) during the Weeks 5-8 assessment period. Therefore, this study will evaluate the benefit of a slightly longer 6-Week treatment period as well as repeating the treatment period for a 12-Week treatment duration. The 6-Week treatment period which is half in duration may still be beneficial and have a better safety profile due to less time on treatment.

For the primary endpoint, success is defined as complete abstinence during the last 4 weeks of treatment with weekly expired CO measurements ≤ 10 ppm for both 6- and 12-Week cytisinicline treatment durations plus behavioral support (Arm B and Arm C, respectively) compared to placebo plus behavioral support (Arm A).

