 - b. If subject has smoked, subject should report the total number of cigarettes smoked since the last clinic visit.
 - c. Has the subject used any non-cigarette nicotine products, including vaping, since the last clinic (Day 70) visit? If yes, record what was used and remind subject such products should not be used during the study.
8. Remind subject of their Day 84 (Week 12) appointment date and time and that they must bring with them their study treatment packs.

Treatment Day 86/ Week 12 (Assessment Day 86 ± 1)

Note: The final day of treatment should be on Day 84. In order to ensure all subjects have completed treatment prior to assessments, the Week 12 visit is to be scheduled on Day 86 ± 1 day.

1. Administer and assess suicidal ideation/risk using the “Since Last Visit” C-SSRS (refer to [Appendix 1](#)).
2. Subject to complete the HADS questionnaire ([Appendix 6](#)).
3. Review study treatment diary to verify dosing through Week 12.
4. Assess for AEs and any changes to concomitant medications.
5. Vital signs, including weight.
6. Review study treatment Week 12 pack for compliance and collect both Weeks 11 and 12 packs (which should be empty if all doses were taken as expected).
7. Provide subject with behavioral support information that includes counseling ([Appendix 7](#)).
8. Blood for hematology, serum chemistry and cotinine testing.
9. Urine pregnancy for all female subjects, excluding those that are surgically sterile (hysterectomy or tubal ligation) or >2 years post-menopausal.
10. 12-lead ECG.

11. Expired CO.
12. Record the following:
 - a. Has the subject smoked any cigarettes since the last clinic (Day 77) visit?
 - b. If subject has smoked, subject should report the total number of cigarettes smoked since the last clinic visit.
 - c. Has the subject used any non-cigarette nicotine products, including vaping, since the last clinic (Day 77) visit? If yes, record what was used and remind subject such products should not be used during the study.
13. All subjects, regardless of smoking status, are to be scheduled for their Week 16 (± 3 days) follow-up visit.

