16.4.1. Analysis of Secondary Outcomes

There are 3 secondary efficacy objectives, 2 objectives for continuous abstinence and 1 objective for reduction in risk of relapse. The continuous abstinence through Week 24 success outcome (secondary objectives 1 and 2) and relapse-free through Week 24 (secondary objective 3) must be defined separately for each of the three associated comparisons because of differences in the primary evaluation timing, that is, Weeks 3-6 for the Arm A versus Arm B comparison and Weeks 9-12 for Arm A versus Arm C comparison, and a mixed primary evaluation time for the Arm B versus Arm C comparison. It is important to note that the data collected and the schedule of collection are identical for all arms.

The following operational details are applicable to these secondary comparisons:

- Being abstinent requires meeting both a self-reported criterion and a biochemical verification. The beginning of self-reported abstinence is Week 3 to Week 6 for comparisons of Arm A and Arm B and Week 9 to Week 12 for comparison of Arm A and Arm C. For comparison of Arm B to Arm C, the failure of self-reported abstinence starts at Week 6 for both Arms B and C.
- Self-reported abstinence over the Follow-up Weeks 16-24 period will be assessed using the Russell Standard¹⁷ to be regarded as abstinent or without relapse.
- Biochemical verification of non-smoking status is defined by a carbon monoxide concentration in exhaled breath of less than 10 ppm.

Subjects not observed to meet all success criteria will be regarded as non-success relative to the secondary efficacy outcome. Non-success will have two types: (1) subjects with adequate data that fail to meet the above criteria, and (2) subjects having insufficient data to be assessed as a success.

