3.2. Secondary Efficacy Objectives

The analysis for secondary objectives 1 and 2 will be done only if the corresponding primary comparison passes statistical criterion.

1. Assess whether subjects randomized to Arm B (3 mg cytisinicline TID for 6 weeks followed by placebo TID for 6 weeks plus behavioral support) have a higher probability of continuous abstinence from Week 6 to Week 24 post-randomization as compared to subjects randomized to Arm A (placebo TID plus behavioral support).
2. Assess whether subjects randomized to Arm C (3 mg cytisinicline TID for 12 weeks plus behavioral support) have a higher probability of continuous abstinence from Week 12 to Week 24 post-randomization as compared to subjects randomized to Arm A (placebo TID plus behavioral support).

The analysis for secondary objective 3 will be conditional and performed only if both primary comparisons 1 and 2 pass statistical criterion.

3. Assess for a reduction in risk of relapse (relapse free through to Week 24) from Week 6 to Week 24 in subjects receiving 3 mg cytisinicline for 6 weeks and then either continue 3 mg cytisinicline from Week 6 to Week 12 (Arm C) or were switched to placebo from Week 6 to Week 12 (Arm B). Subjects not abstinent at Week 6 will be regarded as having relapsed.

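### Secondary endpoint 3 (relapse-free, Arm C vs Arm B) has no criterion for the Week 7-11 visits, so recorded smoking there, followed by a re-quit by about Day 77, still counts as relapse-free

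*SAP*

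**What the plan says.** Secondary objective 3 compares Arm C (12 weeks of cytisinicline) with Arm B (6 weeks, then placebo). SAP 3.2 states it as "Assess for a reduction in risk of relapse (relapse free through to Week 24) from Week 6 to Week 24". The protocol synopsis says that relapse among Weeks 3-6 abstainers "will be compared in Arm C vs Arm B from Week 7 to Week 24". Protocol 16.4.1 adds: "For comparison of Arm B to Arm C, the failure of self-reported abstinence starts at Week 6 for both Arms B and C".

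The working definition is in SAP 4.1.2.2. After Weeks 3-6 success, a subject must meet two criteria. The first is "At the Week 12 visit, subject self-report of abstinence (relapse-free) since the last clinic visit together with biochemical verification of abstinence, and" and the second is the Week 16-24 follow-up, with at most five cigarettes in total and CO verification at each attended visit. Anyone not meeting these criteria has relapsed.

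For the parallel endpoint 1 (Arm B vs Arm A, Week 6 to Week 24), SAP 4.1.2.1 has one criterion more: "At the Week 7 to Week 11 visits, subject self-report of abstinence since the last clinic visit together with biochemical verification of abstinence, and".

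The question that is put to subjects in Week 12 is "Has the subject smoked any cigarettes since the last clinic (Day 77) visit" (Protocol 12.2.3).

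**The concern.** The list in SAP 4.1.2.2 is closed: relapse means failing a listed criterion, so an event at an unlisted visit cannot be a relapse. Smoking or raised CO recorded at Weeks 7 to 11 has no effect on the outcome if the subject has stopped again by about Day 77.

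Arms B and C differ in assigned treatment only in Weeks 7-12, and the uncovered visits span about five of those six weeks, starting when Arm B switches to placebo. The protocol expects relapse at that point. Section 7.3.2 justifies longer treatment "since smoking relapse appeared high in ORCA-1 from the end of treatment abstinence (Week 4) during the Weeks 5-8 assessment period".

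Endpoint 3 is the only comparison of 12 with 6 weeks that has multiplicity protection (SAP 10.1.1). As defined, a result could not properly be described as relapse-free from Week 6 to Week 24.

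**Working it through.** **1. The plan's own figure.** The only sizing calculation is for each active arm against placebo: 250 per arm, 7% vs 19%, one-sided 0.0125, Fisher's exact test, 95.7% power (SAP 2.2). Exact enumeration over the two binomials gives 95.75%, and the odds ratio is (0.19/0.81)/(0.07/0.93) = 3.116. Both agree with the plan. No rate or power is given for endpoint 3, so everything in steps 4 and 5 rests on assumed rates.

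**2. The criteria side by side.**

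| Visits | Endpoint 1 (SAP 4.1.2.1) | Endpoint 3 (SAP 4.1.2.2) |
|---|---|---|
| Weeks 3-6 | primary success | primary success |
| Weeks 7-11 | self-report and CO | not mentioned |
| Week 12 | self-report and CO | self-report and CO |
| Weeks 16-24 | up to 5 cigarettes, CO | up to 5 cigarettes, CO |

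**3. A test subject in Arm B.** Success at Weeks 3-6; smoking reported, or CO of 10 ppm or more, at one or more of Weeks 7-11; Week 11 visit attended; no smoking from Day 77 to the Week 12 visit, with CO below 10 ppm; Weeks 16-24 criteria met. This subject fails endpoint 1 and has a Week 7-11 failure date in the exploratory time-to-failure analysis (SAP 4.1.3), yet is relapse-free in endpoint 3. If the Week 11 visit was missed, the Week 12 look-back may reach further; otherwise it stops at Day 77.

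**4. Possible effect on the comparison.** Take the rate that counts Week 7-11 smoking as relapse, and add the hidden re-quitters (percentage points) to get the rate as the SAP would score it. Unstratified Fisher test, 250 per arm, one-sided 0.025.

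| True rate, B vs C | Hidden, B / C | Scored, B vs C | Odds ratio | Rejection probability |
|---|---|---|---|---|
| 10% vs 17% | 0 / 0 | 10% vs 17% | 1.84 | 59% |
| 10% vs 17% | 3 / 1 | 13% vs 18% | 1.47 | 30% |
| 10% vs 17% | 2 / 2 | 12% vs 19% | 1.72 | 54% |
| 10% vs 17% | 1 / 3 | 11% vs 20% | 2.02 | 77% |
| 12% vs 12% | 0 / 0 | 12% vs 12% | 1.00 | 1.8% |
| 12% vs 12% | 1 / 3 | 13% vs 15% | 1.18 | 7.6% |
| 12% vs 12% | 3 / 1 | 15% vs 13% | 0.85 | 0.3% |

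For equal true rates from 10% to 17%, hidden shares of 1 / 3 give a rejection probability of 6.7% to 8.0%.

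**5. How large the hidden group might be in Arm B.** In the sponsor's Phase 2b trial, point abstinence at Week 4 was "48% and 50% for the 1.5 mg and 3 mg TID arms, respectively, compared to 10% for the placebo arms" (Protocol 4.3). The 3 mg TID arm had 30% continuous abstinence over Weeks 5-8. So at least (50 - 30)/50 = 40% of Week 4 abstainers did not meet continuous abstinence in the four weeks after treatment. Assume that 30% of Arm B are abstinent at Weeks 3-6 and that 40% of them fail in Weeks 7-10: 250 x 0.30 x 0.40 = 30 subjects. If 5% to 25% of those re-quit by Day 77 and hold, the misclassified number is 30 x 0.05 = 1.5 to 30 x 0.25 = 7.5, or 0.6 to 3.0 points.

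**The case against.** The strongest reply is that the text is ambiguous. SAP 4.1.2 says that, for Arm C against Arm B, failure of self-reported abstinence starts at Weeks 3-6, and 4.1.2.2 itself opens with Weeks 3-6 through Week 24. A programmer might count Week 7-11 smoking on that basis. But these lines say when failure can start and set no rule for any Week 7-11 visit, while the list that decides classification omits those visits. They sharpen the conflict without resolving it.

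The leniency could also be deliberate. Protocol 16.4 and the synopsis speak of being without relapse at Week 24, and the counselling text treats lapses as recoverable. However, no passage states a lapse allowance before follow-up; the five-cigarette allowance is confined to Weeks 16-24. Read literally, the endpoint permits unlimited smoking from Week 6 to Day 77, none from then to the Week 12 visit, and up to five cigarettes afterwards. No rationale is given for that pattern.

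It is true that time to failure, weekly point prevalence and other objective 7 (continuous abstinence at Week 24, Arm C vs Arm B, among Weeks 3-6 abstainers) would show some of the early relapse. These analyses are exploratory and do not repair the protected one.

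The objections to the size stand in part. The Phase 2b figure concerns smokers who had stopped treatment after 25 days and starts from a seven-day measure, so it is only a rough guide to Arm B and says nothing about Arm C. The re-quit range has no source. Three points in Arm B is the top of the range in step 5; at 0.6 points in each arm, power falls only from 59% to 57%. Endpoint 3 is also tested with protection only if both primary comparisons and secondary endpoints 1 and 2 succeed.

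**Conclusion.** The concern holds. The omission and its consequence for classification follow from the text and need no assumption beyond attendance at the Week 11 visit. The SAP definition does not match its own objective, the protocol's statement of when failure starts, or the parallel rule for endpoint 1, although SAP 13 reports no change from the protocol's planned analyses.

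The size and direction cannot be derived from the documents. The effect ranges from slight, if re-quitting is rare and balanced, to large if it differs between arms by about two points. Bias in either direction is possible, including a rejection rate above the nominal 2.5% when there is no true difference. Only subjects who lapse and re-quit are affected; study success and the placebo comparisons are untouched. This should be clarified before unblinding.

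**What to change.** Before unblinding, add the Week 7-11 criterion of SAP 4.1.2.1 to 4.1.2.2, so that reported smoking or CO of 10 ppm or more at any of these visits is a relapse. State one missed-visit rule for Weeks 7-11 and apply it to endpoints 1 and 3. At present 4.1.2.1 requires these visits to be observed and lets only Week 16 or Week 20 be missing, while 4.1.2.2 is silent on Weeks 7-11. The choice matters, because importing the wording without a rule would turn a missed visit into a relapse.

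If the sponsor does mean to allow lapses in Weeks 7-11, the SAP should say so and give the reason, reword the objective, and report the strict version as a sensitivity analysis.

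The cost is SAP wording and a decision on missed visits. Smoking status and CO are already collected at every Week 7-11 visit in all arms. Expect somewhat fewer successes in both arms. The analysis set and the site-stratified exact test stay as planned.
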